8.4.3 Treatment Stopping Rules

The trial may be prematurely discontinued by the Sponsor, Chief Investigator or Regulatory Authority on the basis of new safety information or for other reasons given by the Data Monitoring & Ethics Committee / Trial Steering Committee, regulatory authority or ethics committee concerned.

If the trial is prematurely discontinued, active participants will be informed and no further participant data will be collected. The Competent Authority and Research Ethics Committee will be informed within 15 days of the early termination of the trial.

9 Participant timeline

With reference to the internal pilot as well as the RCT, the end of the trial will be defined as last patient last visit. Each individual subject will remain in the trial until the final visit, at month 7. This date will be 30 days after the study end-point (day 182). The total duration from first patient first visit to last patient last visit is anticipated to be 42 months.
10 Sample size

10.1. Proposed sample size:

1) Pilot study: 60 randomised within 12 months of the start of patient recruitment;

2) RCT: 300 hundred CHR-APS patients; n=150 per treatment arm

10.2. Sample size justification:

1) **Internal Pilot:** There was no powered sample size calculation for the internal pilot, the number is instead in line with suggested sample sizes for pilot and feasibility studies and is sufficient to estimate feasibility outcomes.

2) Phase IIB RCT

Justification of Effect Size (ES=0.4)

In our proof-of-concept studies, in which the effect size for 3 weeks of treatment with CBD (Mean change \pm SD: 12.87 \pm 12.8) compared to placebo (Mean change \pm SD: 7.64 \pm 12.6) on psychotic symptom severity was found with a standardised mean difference of 0.41.

The RCT has been powered for the primary outcome. For a novel intervention for CHR patients to be clinically meaningful, we have assumed that its effect-size should be comparable to, or greater than that of CBT, the treatment currently recommended for this group in the NICE guidelines ¹³. The effect size for the change in the severity of psychotic symptoms after 12 months of CBT in the trial by Morrison et al ¹² was 0.39 (estimated as standardized mean difference).

Sample Size Calculation

We estimated that to have 80% power to detect a difference between CBD and placebo on symptom severity at 6 months with an effect size of 0.4, using a two-sided t-test at p=0.05, would require a sample size of n=100 per treatment arm. There was a drop-out rate of 32% reported by Morrison et al ¹². After inflating the sample size by this, we would need to recruit 300 participants for a minimum of 80% power.

10.2.2. Recruitment rate:

Out of 1980 eligible patients across all of our recruitment sites, we expect to screen a majority (around 85%) of those at each centre.

We anticipated a staggered recruitment of the sites as well as requiring three months to maximise recruitment at each site. However, by 1 year after opening our first site, we anticipated to experience our maximum consent and randsomisation rate across all sites.

At this time we anticipate a minimum of 20% (n=28, per quarter) of those screened will be randomised (See 'Plan of Investigation and timetable').

11 Assignment of interventions

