8.4.2 Procedures for Recording and Reporting Adverse Events

The Medicines for Human Use (Clinical Trials) Regulations 2004 and Amended Regulations 2006 gives the following definitions:

Adverse Event (AE): Any untoward medical occurrence in a subject to whom a medicinal product has been administered including occurrences which are not necessarily caused by or related to that product.

Adverse Reaction (AR): Any untoward and unintended response in a subject to an investigational medicinal product which is related to any dose administered to that subject.

Unexpected Adverse Reaction (UAR): An adverse reaction the nature and severity of which is not consistent with the information about the medicinal product in question set out in:

The Investigator's Brochure (IB) relating to the study.

Serious adverse Event (SAE), Serious Adverse Reaction (SAR) or Suspected Unexpected Serious Adverse Reaction (SUSAR): Any adverse event, adverse reaction or unexpected adverse reaction, respectively, that

> Results in death; Is life-threatening; Required hospitalisation or prolongation of existing hospitalisation; Results in persistent or significant disability or incapacity; Consists of a congenital anomaly or birth defect.

Important Medical Events (IME) & Pregnancy

Events that may not be immediately life-threatening or result in death or hospitalisation but may jeopardise the patient or may require intervention to prevent one of the other outcomes listed in the definition above should also be considered serious.

Although not a serious adverse event, any unplanned pregnancy will also be reported via the SAE reporting system. Women who become pregnant within the study will be followed up with evaluation of the pregnancy, foetus and child.

Time period for collection of adverse events

AEs will be recorded from the randomisation visit to the final safety visit (day 212). Any AEs that are unresolved at the follow-up visit in the study will be followed up by the

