12.1 Data collection

Assessment and collection of baseline, outcome and other trial data will be performed as reported in Visit assessments. A detailed description of study instruments is also provided in 8.2 Assessment of Efficacy and 8.3 Procedures for Assessing Efficacy Parameters, they are also included within the Appendix, alongside their scoring algorithms, and coding of missing data.

Whenever possible, follow-up data will be collected independently of study intervention discontinuation. The only occasion in which follow-up data will not be collected is described in 6.6.1 Withdrawal from study Category of withdrawal I (if a participant expresses the wish to be completely withdrawn from the study).

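### Protocol section 8.4.3 ends all participant data collection on early termination, with no exception for the safety data that other sections promise

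*Protocol*

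**What the plan says.** Section 8.4.3 allows the trial to be stopped early "on the basis of new safety information or for other reasons given by the Data Monitoring & Ethics Committee / Trial Steering Committee", or for reasons given by a regulator or ethics committee. If that happens, "active participants will be informed and no further participant data will be collected". The sentence carries no exception.

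Other sections set out what is to be collected:

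- Section 8.4.2, adverse-event period: "AEs will be recorded from the randomisation visit to the final safety visit (day 212").
- Section 8.4.2, pregnancy: "Women who become pregnant within the study will be followed up with evaluation of the pregnancy, foetus and child".
- Section 8.4.2, reporting: all serious events are reported, and the participant is followed until the event has an outcome.
- Section 8.4.1: the safety measures taken at screening, including safety bloods, are repeated at Visit 3 or at withdrawal.
- Section 9: "Each individual subject will remain in the trial until the final visit, at month 7", and "This date will be 30 days after the study end-point (day 182").
- Section 12.1: "Whenever possible, follow-up data will be collected independently of study intervention discontinuation". It adds: "The only occasion in which follow-up data will not be collected is described in 6.6.1 Withdrawal from study Category of withdrawal I", meaning a participant who asks to leave the study completely.

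**The concern.** A stop for new safety information is one of the named triggers in 8.4.3. In that event, participants already dosed are the people whose later adverse events and exit tests would help explain the stop. An instruction to collect nothing further would remove those data, and no analysis can recover what was never recorded. The statistical analysis plan cannot repair this either, because the rule is an instruction to sites about data collection.

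The protocol also treats one participant and the whole trial differently. Under section 6.7.2, a participant whom the investigator withdraws because of a serious event stays on the same assessment schedule to six months. If the same event stops the trial, data collection ends for everyone.

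**Working it through.** **1. The adverse-event window.** Day 182 (study end-point) + 30 days (section 9) = day 212, which matches sections 7.5, 8.4.1 and 8.4.2. The window is stated consistently, so the conflict is between rules and not between figures.

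**2. The rules side by side, for a participant on treatment when the trial stops.**

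| Item | Promised in | Under 8.4.3 read literally |
|---|---|---|
| New non-serious adverse events to day 212 | 8.4.2 | Not collected |
| Exit examination and safety bloods | 8.4.1 (Visit 3 or withdrawal) | Not collected; the protocol does not say whether termination counts as withdrawal |
| Pregnancy follow-up | 8.4.2 | Not collected, or unclear |
| Serious events followed to outcome, SUSAR reporting | 8.4.2 | Not expressly suspended; relation unstated |
| Unresolved adverse events | 8.4.2 | Clinical follow-up only, and only for events unresolved at the follow-up visit, without further entry in the source data worksheet |

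**3. A concrete case.** Section 8.4.2.2 lists raised liver transaminases as potentially related to the intervention. The flowchart (section 4.3) and section 8.4.1 schedule liver function tests at screening and Visit 3; 8.4.1 adds withdrawal. If a participant's treatment ends with the trial before Visit 3 and 8.4.3 is applied literally, no scheduled liver result after the first dose is recorded.

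**4. How many participants (illustration).** Number in a window = randomisation rate × window length. Section 10.2.2 gives 28 per quarter at the maximum rate, so 28 / 91.25 days = 0.307 per day.

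- On treatment: 0.307 × 182 = 56.
- In the 30 days after: 0.307 × 30 = 9.
- Whole window: 0.307 × 212 = 65, and 65 / 300 = 22% of the planned sample.

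This assumes steady state and no dropout.

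**5. Sensitivity.**

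- Even recruitment of 300 over an assumed 24 months: 300 / (24 × 30.44) × 212 = 87. This needs 300 / 8 = 37.5 per quarter, faster than the stated rate.
- Over an assumed 35 months (42 months in total less 7): 300 / (35 × 30.44) × 212 = 60.
- If the 32% dropout used in section 10.2 all left at once: 65 × 0.68 = 44.
- At the 12-month feasibility point, section 8.1 expects 60 randomised and 20 with six months completed: 60 − 20 = 40 still short of six months.

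**The case against.** The best defence is that section 8.4.2 describes the ordinary schedule and 8.4.3 a specific contingency, and that a specific rule normally governs. That reading is possible, but the protocol does not state it. If it is the intended reading, the loss of safety data is intended too, and that should be said openly.

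Three stronger readings are tempting, and the documents do not support them.

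- **Section 12.1 flatly contradicts 8.4.3.** Its statement about the only occasion without follow-up comes directly after a sentence on participants who discontinue the intervention. In context it mainly distinguishes stopping medication from leaving the study in a running trial. It sits uneasily with 8.4.3 but is weaker evidence than section 8.4.2.
- **Serious events would go unreported.** The duties in section 8.4.2 to report serious events and SUSARs, and the SUSAR time limits, are not expressly suspended, and pregnancies are reported through the same system. The clearer exposure is new non-serious events and scheduled exit safety tests.
- **The protocol breaks a promise to keep collecting efficacy outcomes after termination.** Apart from the disputed sentence in 12.1, no section addresses outcome collection once the trial itself has been stopped. A closing CAARMS assessment would be an additional interview by a trained rater (section 8.3.1), not a correction of wording.

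It is also fair to object to any claim that 65 participants are exposed at all times. The figure holds only at the peak rate in steady state. Data already collected are not affected.

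**Conclusion.** The point holds as a conflict about safety data. Section 8.4.3 states without exception a rule that, if followed, ends adverse-event recording and exit safety testing in participants already dosed. It cannot be squared with sections 8.4.1 and 8.4.2 without a statement that the protocol does not contain. For serious events and SUSARs, the finding is only that the relation to 8.4.3 is unstated.

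The size is illustrative: about 65 participants inside their window at the stated peak rate, assuming steady state and no dropout, and fewer early or late in recruitment. The conflict itself does not depend on that count.

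**What to change.** Reconcile section 8.4.3 with sections 8.4.1, 8.4.2 and 12.1. Limit its sentence so that early termination does not end the safety data collection already promised for dosed participants: recording of adverse and serious adverse events, pregnancy follow-up, and the exit safety measures. State how long each continues after termination; the adverse-event window is counted from randomisation, so a participant stopped early could have most of it still to run. Say whether termination counts as withdrawal for the exit measures, and that the duties to report serious events and SUSARs continue. When section 12.1 is edited, correct its cross-reference too: it cites 6.6.1, but withdrawal from the study is section 6.7.1.

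The cost is a protocol wording change and a small amount of site work after a stop. Most of that work is medical-records review, which section 7.5 already plans for the final safety visit; the exit tests are those already listed in section 8.4.1. A closing outcome assessment for participants who agree is optional and not part of this correction.

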11.1 Allocation

11.1.1 Sequence generation and Allocation concealment mechanism

The randomisation service will be provided by the bespoke online randomisation system managed by the King's Clinical Trials Unit (KCTU) such that randomisation information is concealed from the study researchers. Given the large sample size, the allocation sequence will be generated using a random permuted block design (block sizes of 4 to 12), stratified by site. The sequence will be held within a web-based system and concealed from the investigators including the chief investigator and trial statistician.

11.1.2 Implementation

The system is online and can be accessed 24 hours a day. Researchers within the study team log in, enter key information about the participant, and the randomisation allocation occurs instantly. Confirmation emails are generated automatically and sent to the Pharmacy personnel in the study team.

The Trial manager, under the direction of the study team, provide user access to the study sites, and withdraw access at the study conclusion.

11.2 Blinding

11.2.1 – Definitions

In line with KCTU Standard Operating Procedures (SOPs) on blinding.

Fully blinded: Not able to review any post Baseline outcome data coded as CBD/Placebo, or coded as A/B. All data should be presented aggregated across both allocation groups.

Partially blinded. Able to review data post Baseline outcome data as A/B

Unblinded: Able to review post Baseline outcome data as CBD/Placebo

11.2.2 Blinding of Personnel

Throughout the chief investigator, and senior statistician will be fully blind to treatment allocation and will only see pooled data for the duration of the trial. At the start of any TMG/TSC/DMC, the committee are to be reminded the CI and Senior statistician are fully blind and the need to present aggregate data to maintain this.

The Junior Statistician will be fully blind until the first version of the Statistical Analysis Plan (SAP) is approved by the TSC. The SAP should be detailed enough so that it presents a clear and structured plan for the primary outcome, required data manipulation, and analysis. It should be written consistent with the KCTU Statistics SOP on generating a SAP (ST-03 Statistical Analysis Plan). All changes to the SAP after approval by the TSC should be authored by a statistician who is fully blind, this would be expected to be the Trial statistician ([name]). Any amendments to the SAP will be approved by the TMG, and TSC.

After the first version of the SAP is approved by the TSC, the Junior statistician is

planned to become partially-blinded and access patient level data coded as A/B. They will present the closed DMC report to DMC members.

The trial manager is planned to be unblinded in order to expedite safety data from site PI to the Chair of the DMC. The Trial manager will not take part in any discussion that influences any decisions regarding early stopping of the trial.

11.3 Circumstances under which unblinding is permissible

11.3.1 Emergency Code Break

Twenty-four hr Emergency Code Break and Medical Information will be provided by ESMS Global Ltd through their 24-hour code-breaking service (along with emergency medical advice).

11.3.2 Serious health risk and unblinding

Each randomised subject will be provided with a card detailing code break telephone numbers and emergency contact details. Subjects will be requested to carry this card with them at all times whilst participating in the trial. While there is a wide margin of safety with regard to the dose of CBD used in this study, in case of overdose, study participants will be advised to attend the nearest A&E, carrying the emergency contact details card. They will be advised to notify the relevant study team as soon as possible. The contact details of the study team and ESMS Global Ltd (who will provide the emergency code-break service) will be on the emergency contact details card with advice for the treating physician to get in touch in case of overdose or other medical emergency that may require unblinding. In case of overdose, symptomatic and supportive treatment is advised. Evaluation will be also made whether to proceed with the withdrawal of the subject from the study/ study intervention as well as the unblinding.

In the circumstance unblinding is required, all care shall be taken to ensure that the study team are kept blinded. The unblinding procedure will be performed by the Clinical Trials Pharmacy (as named on the Delegation Log).

Details of any emergency unblinding shall be documented fully in the Sponsor file(s), Investigator file(s) and Site file(s). This includes but may not be limited to: 1) Date, 2) Subject details, 3) Reason for unblinding, 4) Name and role of the individual requesting the unblinding, 5) Name and role of the individual carrying out the unblinding. Details will NOT include the results of the unblinding and will also be included in the statistical report.

ESMS Global Ltd through their 24-hour code-breaking service [contact]

12 Methods

12.1 Data collection

Assessment and collection of baseline, outcome and other trial data will be performed as reported in Visit assessments. A detailed description of study instruments is also provided in 8.2 Assessment of Efficacy and 8.3 Procedures for Assessing Efficacy Parameters, they are also included within the Appendix, alongside their scoring algorithms, and coding of missing data.

Whenever possible, follow-up data will be collected independently of study intervention discontinuation. The only occasion in which follow-up data will not be collected is described in 6.6.1 Withdrawal from study Category of withdrawal I (if a participant expresses the wish to be completely withdrawn from the study).

12.2 Source Data

All source data will the held-on paper as a paper source data worksheet (SDW). These will be held locally under the care of the recruiting and consenting site PIs.

12.3 Data management

Data will be collected in paper source data worksheet (SDW) which will then be recorded on a web-based commercial data entry system (InferMed MACRO) hosted by King's Clinical Trials Unit (KCTU). The system is compliant with FDA 21 CFR part 11 and Good Clinical Practice (GCP). It is an appropriate system to use for medicinal trials falling under the Medicines for Human Use (Clinical Trials) Regulations 2004 and its subsequent amendments and has also been used for other complex intervention trials. The web-based system can usually be accessed 24 hours a day and will be accessible to study teams at different sites and allow data entry to run in parallel with patient recruitment and visits.

12.4 InferMed MACRO Database

The InferMed MACRO database will be developed by a KCTU database programmer. Prior to the KCTU developer being assigned, KCTU will be provided with the approved protocol by HRA. The database will be developed and follow a structured two stage process where the chief investigator and Senior statistician will generate and approve the sign off the data collection tools.

The database specification will be validated, and user acceptance tested and confirmed, prior to any patients being consented for this study, by the chief investigator and senior statistician.

Any changes to the specification of the database after the approval of the database will require documentation of the need to be changed, for example an updated protocol amendment from the Health Research Authority.

12.5 Data verification

At the start of the study, a structured data verification plan will be agreed and developed by the Junior statistician and approved by the TMG. The data verification checks will include one-way tabulations of: baseline; and outcome data, range checks, as well as two-way tabulations of multiple item responses. Dates will also be checked for consistency across form completion times.

A data extract will be requested 6 to 8 weeks before a DMC report and unreliable data/ data queries will be raised and circulated by the Junior Statistician, to the Trial Manager to be resolved prior to the DMC report (where possible).

12.6 Central Statistical Monitoring

Part of the data verification plan will include typical central statistical monitoring. This will include, looking at the distribution of the following across the sites: AEs; patient severity level; withdrawal; and dates of Baseline; and outcomes ⁷².

12.7 Data Lock

At the conclusion of the trial: The study team will have resolved the data queries and request to remove user access from KCTU to ensure that the final dataset can not be changed.

12.7.1 Archiving

At the conclusion of the trial, the final MACRO database will be archived on paper in the Trial Master File, alongside all of the essential Trial documentation. This will include all analysis code to reconstruct each of the DMC reports, as well as the final statistical report.

12.8 Data Security and backup

There are systems in place to secure the data collection system against permanent loss and allow the recovery and restoration in the event of such a loss occurring.

12.9 Statistical methods

A Statistical Analysis Plan will be approved by the TSC within the first stages of the Study, and before any partially blinded data is summarised by either the Junior or Senior Statistician.

12.9.1 Baseline Data

Descriptive of baseline data for each study site will be provided in published reports.

12.9.2 Internal Pilot

No statistical analyses will be performed for the pilot study (feasibility data), proportions will be presented for each feasibility outcome.

12.9.3 Population under investigation

The analyses will follow an the intention-to-treat (ITT) principle. All participants will be analysed as part of the treatment arm they were allocated to unless a participant withdraws from the study and requests all previous data to be deleted. Or a patient is randomised and does not complete any post-baseline data.

